**The first study visit** (2 hours) will occur at the BSWH center at which they were initially given the diagnosis of CRC. This visit will occur after consent (after colonoscopy and stool collection at baseline) and screening has occurred and prior to surgery or anti-cancer treatment is initiated. For stool samples, subjects will be given a bag with collection devices, a **Stool Collection History Form**, and instructions (**Comprehensive Stool Kit FED EX Ready**) for collecting stool and contacting the REA for stool drop off or pick up (**instruction for Retraining Your Specimen Samples**). The patients will also be provided with a mailer box if they would rather mail in their specimen, which is stable on ice packs (provided with stool kit) for 24 hours. Prior to Visit 2, patients will complete 2 online dietary assessment tools, the food frequency questionnaire called the **DHQIII (an online survey that takes 30-60 minutes)** and **24-hour recall called the ASA24 (an online survey that takes 20-30 minutes)**, at home prior to their outpatient visit (after surgery) and prior to the beginning of treatment. If the participant needs assistance with either of these surveys, the REA will guide the patient through the online assessment from their computer. This dietary assessment tool is well validated and has been used in numerous large population studies for collection dietary pattern information. Participants will also complete a medical history questionnaire (**COLON-MD Questionnaire 2020-2023**) in an interview with one of the BSW REAs at the time of their first visit.

On the day of surgery, blood will be collected as part of SOC. During surgery, tissue will also be collected from resection, tumor and non-tumor adjacent (2 of each; one for frozen and one for fixation).

**The second study visit** (1 hour) will take place approximately three to four weeks (weeks 3 or 4) after surgery in the outpatient clinic. During this study visit, an additional 2 vials of blood will be taken at the same time as part of the routine clinical visit, and the patient will be given another stool sample kit to take home to collect stool and instructions. The patient will again be asked to take the 24-hour recall online (**ASA24**) complete it at home online within 72 hours of producing the stool sample, and complete the **Stool Collection Form**.

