The stool samples collected and stored in 95% ethanol will undergo metabolite analysis (using the iHMP protocol; <https://ibdmdb.org/cb/browser/Clinical%20Protocol>) in the laboratory of [name] (Collaborator, BU) using high-performance liquid chromatography for SCFAs and indoles according to previous methods, as well as, putative metabolites identified from the PIPHILLIN algorithm. We will use a chromatographic approach based on Tuomola et al., to quantify these indoles and their other analogs. Stool samples will also be analyzed for SCFA (acetic acid, propionic acid, butyric acid, isobutyric acid, valeric acid, and isovaleric acid) with liquid chromatography associated to mass spectrometry.

*Circulating Cytokines:*

Levels of circulating cytokines at baseline (prior to surgery), prior to FOLFOX (treatment naive), and during treatment will be captured at the same time as regular blood draws to minimize patient risk and discomfort. Clinical staff will be provided with labels for each patient attached to their chart to apply to the tubes at the time of blood draw. All clinical specimens will be labeled with the participant code, date of sample acquisition and type of sample (e.g. blood 01), then placed in the clinical laboratory refrigerator within 2h after collection to maintain storage at 4°C until processing serum. Serum samples will be centrifuged and immediately stored at -80°C until shipped to the [name] lab in batch for processing. Cytokine measures will be conducted using the Luminex technology.

*Tissue Biofilm Quantification:*

Invasive biofilms (>200 micrometers) will be assessed after CRC and paired normal tissue is collected from enrolled patients undergoing surgery at Baylor Scott and White. The pathologist will use aseptic techniques to process the tissues immediately after tissue collection. All tissue not needed for pathologic diagnosis will be rapidly preserved in formalin, Carnoy's solution and RNAlater for analysis. For patients in this study, two bowel preparations will be used and recorded (mechanical bowel preparation [MiralaxTM], or Fleet Phospo-sodaTM enema). Pre-operative intravenous antibiotics are administered in all

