cases (cefotetan or clindamycin/gentamycin). Oligonucleotide probes will be synthesized and conjugated at the 5' end to the fluorophore Cy3, Alexa 405, Alexa 488, Oregon Green 514, Alexa 514, Alexa 555, Rhodamine Red X, Texas Red X, Alexa 633 or Alexa 647 (Invitrogen Life Technologies). Twelve probes will be applied to 5  $\mu$ m thick Carnoy's solution-fixed paraffin-embedded tissue sections. All samples collected will also be stained with the Eub338 universal bacterial probe to detect all bacteria present on the sample. Successive sections will be stained with Periodic acid Schiff (PAS) to confirm mucus presence and preservation. Samples that are determined to have a bacterial presence by universal probe will be analyzed using group and species specific probes. Slides will be de-waxed following standard procedures. Probes will be applied to slides at a concentration of 2 pmol/ul in prewarmed hybridization buffer (900 mM NaCl, 20 mM Tris pH 7.5, 0.01% SDS, 20% formamide). Slides will be incubated at 46°C in a humid chamber for 2 hours, and washed at 48°C for 15 minutes in wash buffer (215 mM NaCl, 20 mM Tris pH 7.5, 5 mM EDTA). Slides will be dipped in water, then in 100% ethanol, air-dried, and coverslips mounted using ProLong Gold antifade reagent (Life Technologies). Biofilm bacterial density and depth will be measured using slides hybridized with the universal bacterial probe, Eub338, and imaged at 1000x magnification with a Nikon E800 microscope and Nikon NIS elements viewing software.

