#### **4.4 Data Analysis.**

Classification of taxa associated with side effects or severity: Recently, in an animal model of colon tumorigenesis (AOM/DSS), investigators used the initial microbial community structure (16s rRNA sequencing) to predict tumor burden after exposure to various antibiotics during colon carcinogenesis. In order to conduct a similar analysis and reduce data dimensionality, we will first perform cluster modeling using Dirichlet multinomial mixtures (Holmes et al. 2012) to identify microbial clusters (community state types). To determine which taxa or taxonomic cluster are the best predictors of treatment side effects (CID, mucositis) and severity (stage 3-4), we will conduct 10-fold cross-validation using the RandomForest package (Version 3.6.4) in R (R-studio, Version 0.98.1091; Boston, MA). Specifically, 5,000 trees will be used and the parameter mtry will be set at 100. The taxa with the highest importance scores will be used for further analysis. This procedure will be tested by splitting the data into test and training sets, then running Random Forest using the same procedure described above on the training dataset and comparing the predictive accuracy of the top taxa (based on importance scores) in the test set. Based on this 10-fold cross-validation, we will be able to calculate sensitivity and specificity. These top taxa will then be used to generate receiver operator curves (ROC) and calculate area under the curve (AUC). Each microbial cluster or taxa will undergo independent logistic regression testing to calculate area under the ROC curve using Stata (v13). The command roccomp will be used to compare statistical difference between AUCs and determine the best combination of taxa for classification of CID or mucositis and for severity.

Microbiome-Diet Analysis: To evaluate the impact of diet on the stool and tissue microbiome, we will use the dietary analysis generated from the ASA24 and DHQIII, which includes the Healthy Eating Index (HEI). Prior to analysis, we will conduct normality testing for each variable using Shapiro-Wilk test. For any variables that do not pass, a logarithm transformation will be performed. In order to identify any potentially important diet or nutrient-microbiome associations, we will conduct correlation analysis between dietary macronutrients (carbohydrates, fats, proteins) or micronutrients (vitamins and minerals)

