and microbial clusters (community state types) at baseline using Kruskall-Wallis, and for individual taxa using Pairwise Spearman correlations. We will use PERMANOVA for comparing beta-diversity (weighted UniFrac distances) at baseline by levels of macro- and micronutrients. DESeq2, Kruskall-Wallis and Mann-Whitney tests will be conducted to identify significant differences in tissue and stool taxa or microbial clusters according HEI scores at baseline. The Benjamini and Hochberg false discovery rate (FDR) will be used to correct for multiple testing. Taxa or microbial clusters found to be significantly differentially abundant between treatment time points and baseline will be used to conduct 'random forest' modeling, as previously described, to identify dietary factors that best predict changes in these taxa or clusters. Additionally, we will investigate the tissue and stool microbiome-diet relationship using principal components analysis to identify significant trends among the dietary factors using coinertia analysis. To investigate the microbiome-diet relations during treatment, we will use the microbial clusters and calculate the  $\log_2$  fold change in the clusters from baseline. We will then determine how much the clusters change from baseline according to dichotomous values of macronutrients.

**Microbiome-treatment analysis:** To evaluate differential abundance comparing treatment time points to baseline (prior to surgery and post-surgery/pre-treatment), DESeq2 will be used to control operational taxonomic unit (OTU) over-dispersion between replicates; OTUs will be considered significantly differentially abundant between time points if the false discovery rate (FDR) corrected p-value is below 0.1. A change in relative abundance will be defined as a fold change between mean log relative abundance during treatment phase (week 4, 14, 24) and baseline (prior to surgery). Taxa found to be significantly differentially abundant between treatment time points and baseline (FDR corrected p-value  $<0.05$ ) will be put into an adjusted regression model to control for age, education, income level, marital status, and activity level, diet quality (HEI), tumor stage, medical history with p-values corrected for multiple hypothesis testing using FDR adjustment.

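### The exploratory tests of tissue taxa by diet quality name no term for bowel preparation or antibiotic regimen, although tissue is resected after both; adjusting for them is a cheap improvement

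*Protocol*

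**What the plan says.** Four parts of the protocol bear on this.

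- **Exposure before resection.** Data Collection, Tissue Biofilm Quantification, states that "two bowel preparations will be used and recorded". It continues "Pre-operative intravenous antibiotics are administered in all" surgical "cases (cefotetan or clindamycin/gentamycin"). Preparation is therefore a recorded variable with two levels. The antibiotic regimen also has two levels, but the text does not say that it is recorded.
- **Timing of the tissue sample.** Section 4.3, Study procedures: "During surgery, tissue will also be collected from resection". Both exposures come first.
- **The diet analysis.** Section 4.4, Microbiome-Diet Analysis, sets out "To evaluate the impact of diet on the stool and tissue microbiome". Its tests are DESeq2, Kruskal-Wallis and Mann-Whitney, used "to identify significant differences in tissue and stool taxa or microbial clusters according HEI scores at baseline". A false discovery rate correction is specified; no covariate is.
- **The covariate list.** Under Microbiome-treatment analysis, a regression is to "control for age, education, income level, marital status, and activity level, diet quality (HEI), tumor stage, medical history". That list serves the comparison of treatment time points with baseline, and it contains neither preparation nor regimen.

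**The concern.** Elsewhere the protocol takes care over these same exposures. The first stool is to be collected before bowel preparation (section 4.1), antibiotics in the last month are an exclusion (Sample Population), and the Introduction cites murine work in which antibiotics destroyed the microbiome. Tissue cannot be protected in that way. The preparation type is to be recorded, yet nothing in section 4.4 uses it.

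Two things are at stake in the tissue-diet results. If the choice of preparation or regimen goes with diet quality, or with something correlated with it such as site or general health, an effect of preparation could be read as an effect of diet. The false discovery rate correction would not help, because it deals with multiplicity and not with confounding. If the choice is unrelated to diet, the ignored variable only adds noise.

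**Working it through.** The protocol states no figure on this point, so there is nothing to reproduce. The check is a comparison of the text followed by an illustration on stated assumptions.

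**Text.** Tissue is resected after preparation and antibiotics. Three tests are named for tissue by HEI. Kruskal-Wallis and Mann-Whitney in standard form take no covariate. DESeq2 can take one, but no design formula is given. The only covariate list belongs to another contrast.

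**Illustration: inputs.** From the protocol: 112 patients. Assumed:
- tissue from all 112, split 56/56 into high and low HEI;
- one two-level exposure that shifts log abundance by s = 0.5 or 1.0 SD;
- its share differing between HEI groups by d = 0, 0.2 or 0.4, centred on one half;
- no true diet effect; two-sided 5% test.

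**Bias by hand.** The spurious difference is s × d. Its standard error is √(1 + s²p(1 − p)) × √(2/56), with p = 0.5 + d/2. The normal-approximation rejection rate follows from the ratio of the two. The simulated columns come from 5,000 runs per setting, using an unadjusted Mann-Whitney test and a linear model that includes the exposure.

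| d | s | s × d | SE | Ratio | Approximate rejection rate | Simulated, unadjusted | Simulated, adjusted |
|---|---|---|---|---|---|---|---|
| 0 | 0.5 | 0 | 0.195 | 0 | 5.0% | 4.4% | 4.6% |
| 0 | 1.0 | 0 | 0.211 | 0 | 5.0% | 4.4% | 4.7% |
| 0.2 | 0.5 | 0.10 | 0.195 | 0.51 | 8.1% | 7.6% | 5.1% |
| 0.2 | 1.0 | 0.20 | 0.210 | 0.95 | 15.8% | 15.4% | 5.2% |
| 0.4 | 0.5 | 0.20 | 0.194 | 1.03 | 17.8% | 17.1% | 4.6% |
| 0.4 | 1.0 | 0.40 | 0.208 | 1.92 | 48.6% | 48.0% | 5.0% |

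The Monte Carlo standard error near 5% is √(0.05 × 0.95/5000) = 0.3 percentage points, so the adjusted rates are in line with 5%. The hand and simulated figures agree closely.

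**Precision when exposure is balanced (d = 0).** Leaving the exposure out inflates the SD from 1 to √(1 + s²/4), which is 1.031 for s = 0.5 and 1.118 for s = 1.0. At an assumed diet effect of 0.53 SD with 56 per group, power is 80.1% adjusted, against 77.7% and 70.8% unadjusted.

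**The case against.** The strongest reply is that this is an exploratory screen whose covariates could properly be left to a statistical analysis plan that is not shown. Tissue taxa by diet is not among the aims (Aim 2 relates diet to diarrhea) and is not a listed endpoint. DESeq2 is already named and would accept a covariate, and the protocol does say that preparation will be recorded. This stands as a limit on importance. It does not remove the point, because for this comparison the protocol names two tests that cannot adjust, and it gives no use for the variable that it records.

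The lack of evidence on size also stands. Every patient receives antibiotics, so only the difference between regimens can confound. The documents show no link between preparation or regimen and diet, and they give no effect of either on tissue taxa.

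Some stronger readings are tempting and are not supported:
- *That tissue is mislabelled as an unexposed baseline.* The words *at baseline* may belong to the HEI scores, and the exposures are disclosed openly.
- *That tissue and stool are pooled.* They are named in the same sentence, but no pooling is stated.
- *That both exposures are recorded.* This is said of preparation only.
- *That biofilm-by-diet models have the same fault.* The protocol states no such model.

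**Conclusion.** The point holds as a low-severity improvement to the exploratory tissue-diet analysis. The named tests leave out two exposures that precede every tissue sample. The result is confounding if either exposure differs by diet group, and otherwise only a loss of precision. Which of the two applies, and how large it is, cannot be settled from the documents. The range above (from no inflation to 48% per taxon, or a loss of about 2 to 9 points of power) depends entirely on the assumed shifts, imbalances and diet effect, and should be read as an illustration of direction.

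A reader might infer that the tissue-diet results will be biased. The documents do not support that, since nothing in them ties preparation or regimen to diet. The primary diarrhea endpoint and stool collected before preparation are not affected.

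**What to change.** - For tissue taxa and clusters by HEI, make the main test a DESeq2 or regression model with bowel preparation as a term, or a rank test stratified by preparation. Keep the plain rank tests as descriptive.
- Add antibiotic regimen as a second term. Take it from the medical-record review already planned under Medical and Symptom History, and list it as an item to abstract, because its recording is not stated.
- In reports, describe tissue as sampled after preparation and antibiotics, in contrast to stool collected before preparation.

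The cost is about two degrees of freedom in each tissue model and one more chart item per patient. No sample, visit or aspect of care changes.

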#### *Dietary Analysis:*

Subject will complete dietary assessments within a 24 hour window of time of stool collection for each stool collection timepoint listed in figure 1. Through the National Cancer Institute (NCI) ASA24-2016 web-portal, the project PI's will register the study allowing utilization of the free ASA24-2016 Dietary Recall instrument. Study participants will be instructed to complete the ASA24-2016 within 24 hours of stool collection at each time point. Participants will also be provided instructions for login to the ASA24-2014 using their confidential study ID. Similarly, the PI will register the study for use of the FFQ to allow the online use of the Diet History Questionnaire. The study participants will be instructed to also complete the online DHQIII prior to the first FOLFOX treatment. The ASA24-2016 asks about food consumed within the last 24 hours based on the on USDA's Automated Multiple-Pass Method (AMPM). Participants have approximately five screens to detail their food intake with prompts to remember food in between meals, source of preparation for the food and a question that asks if food intake was reflective of the participants' typical diet. The recall is respondent-driven in that the detailed questions asked are based on a series of linked question pathways. ASA24 also does not collect any identifying data directly from respondents. However, IP address information is accessed for the purpose of routing information between the server and the respondent's computer -- often the IP address is that of the user's Internet Service Provider (ISP). IP addresses are not stored or tracked by ASA24. However, logs of connections are kept for audit trail purposes. This information is not mined in any way but would be available if there were a legal obligation to release it. Similarly, the Food Frequency Questionnaire (FFQ) or DHQIII also is usually self-administered and has recently become available as a web-based tool, specifically for the Diet History Questionnaire (DHQ). The DHQ was developed and validated by the NCI in two separate studies. Recently, DHQ III has a food list that has been updated from DHQ I based on more recent dietary data and consists of 134 food items and 8 dietary supplement questions. This web-based version takes <1 hour to complete and can be analyzed with the Diet\*Calc software developed by the NCI. This version will be completed by study participants at the time point prior to FOLFOX treatment.

#### *Medical and Symptom History:*

Specific subject information will be collected via review of the medical record(s). Specifically, data will be collected apart from that captured on the medical record, which will include minimal information on socioeconomic status (education, income), tobacco and alcohol history and medication history (**COLON-MD Questionnaire 2020-2023**). At each clinical visit after surgery and during the treatment time points, the REA will assess mucositis and diarrhea grade using the **CTCAE – Gastrointestinal/Diarrhea, Grade 1-5**.

#### Risks & Benefits:

The benefits of the study are improved survival for patients, less toxicities for patient on chemotherapy, and improved quality of life. Also, this study will help contribute to the growing body of knowledge regarding colon cancer and could help future patients diagnosed with colon cancer. Since we are collecting stool specimens which does not expose patient to any adverse procedures or drug or potential side effects there is very minimal risk, and substantial benefit for the patient and for society in general.

#### Data handling and storage:

The research data will be stored on a secure server at Baylor University. Once samples are collected, identifiers will be removed the Baylor Scott and White clinical research coordinator/staff and only the Study ID will be retained. Subject's data and all sequencing data will be maintained in a coded fashion on secure servers at Baylor University. Subject confidentiality will be strictly held in trust by the participating investigators, their staff, and the sponsor(s) and their agents. This confidentiality will be extended to cover testing of biological specimens in addition to the clinical information relating to participating subjects. The study documentation, data and all other information generated will be held in strict confidence. No information concerning the study or the data will be released to any unauthorized third party without prior written approval of the sponsor. The study monitor or other authorized representatives of the sponsor may inspect all documents and records required to be maintained by the Investigator, including but not limited to, medical records (office, clinic or hospital) and pharmacy records for the subjects in this study. PHI provision will be observed with all patients information will be coded on the study except on consents that only [name] will have access to. Subjects on the study will be given an ID that only the PI will have decoding key to. The nature of the information collected from subjects may involve risk to their privacy.

#### **4.4 Data Analysis.**

Classification of taxa associated with side effects or severity: Recently, in an animal model of colon tumorigenesis (AOM/DSS), investigators used the initial microbial community structure (16s rRNA sequencing) to predict tumor burden after exposure to various antibiotics during colon carcinogenesis. In order to conduct a similar analysis and reduce data dimensionality, we will first perform cluster modeling using Dirichlet multinomial mixtures (Holmes et al. 2012) to identify microbial clusters (community state types). To determine which taxa or taxonomic cluster are the best predictors of treatment side effects (CID, mucositis) and severity (stage 3-4), we will conduct 10-fold cross-validation using the RandomForest package (Version 3.6.4) in R (R-studio, Version 0.98.1091; Boston, MA). Specifically, 5,000 trees will be used and the parameter mtry will be set at 100. The taxa with the highest importance scores will be used for further analysis. This procedure will be tested by splitting the data into test and training sets, then running Random Forest using the same procedure described above on the training dataset and comparing the predictive accuracy of the top taxa (based on importance scores) in the test set. Based on this 10-fold cross-validation, we will be able to calculate sensitivity and specificity. These top taxa will then be used to generate receiver operator curves (ROC) and calculate area under the curve (AUC). Each microbial cluster or taxa will undergo independent logistic regression testing to calculate area under the ROC curve using Stata (v13). The command roccomp will be used to compare statistical difference between AUCs and determine the best combination of taxa for classification of CID or mucositis and for severity.

Microbiome-Diet Analysis: To evaluate the impact of diet on the stool and tissue microbiome, we will use the dietary analysis generated from the ASA24 and DHQIII, which includes the Healthy Eating Index (HEI). Prior to analysis, we will conduct normality testing for each variable using Shapiro-Wilk test. For any variables that do not pass, a logarithm transformation will be performed. In order to identify any potentially important diet or nutrient-microbiome associations, we will conduct correlation analysis between dietary macronutrients (carbohydrates, fats, proteins) or micronutrients (vitamins and minerals)

and microbial clusters (community state types) at baseline using Kruskall-Wallis, and for individual taxa using Pairwise Spearman correlations. We will use PERMANOVA for comparing beta-diversity (weighted UniFrac distances) at baseline by levels of macro- and micronutrients. DESeq2, Kruskall-Wallis and Mann-Whitney tests will be conducted to identify significant differences in tissue and stool taxa or microbial clusters according HEI scores at baseline. The Benjamini and Hochberg false discovery rate (FDR) will be used to correct for multiple testing. Taxa or microbial clusters found to be significantly differentially abundant between treatment time points and baseline will be used to conduct 'random forest' modeling, as previously described, to identify dietary factors that best predict changes in these taxa or clusters. Additionally, we will investigate the tissue and stool microbiome-diet relationship using principal components analysis to identify significant trends among the dietary factors using coinertia analysis. To investigate the microbiome-diet relations during treatment, we will use the microbial clusters and calculate the  $\log_2$  fold change in the clusters from baseline. We will then determine how much the clusters change from baseline according to dichotomous values of macronutrients.

**Microbiome-treatment analysis:** To evaluate differential abundance comparing treatment time points to baseline (prior to surgery and post-surgery/pre-treatment), DESeq2 will be used to control operational taxonomic unit (OTU) over-dispersion between replicates; OTUs will be considered significantly differentially abundant between time points if the false discovery rate (FDR) corrected p-value is below 0.1. A change in relative abundance will be defined as a fold change between mean log relative abundance during treatment phase (week 4, 14, 24) and baseline (prior to surgery). Taxa found to be significantly differentially abundant between treatment time points and baseline (FDR corrected p-value  $<0.05$ ) will be put into an adjusted regression model to control for age, education, income level, marital status, and activity level, diet quality (HEI), tumor stage, medical history with p-values corrected for multiple hypothesis testing using FDR adjustment.

**Community state type modeling of treatment effect:** As described earlier, in order to reduce data dimensionality and improve power (due to small sample size), we will perform cluster modeling using Dirichlet multinomial mixtures, as well as, use the partitioning around the medoid (pam in R) algorithm. To calculate the dissimilarity matrix for this analysis, we will first calculate weighted UniFrac distance, then this matrix will be dimensionally reduced by choosing the most significant eigenvectors from PCoA analysis. Community state types (CST), which are defined as 'clusters of community samples with similar compositions of microbial taxa', will be obtained from this analysis. Statistical difference in CST abundance between treatment and baseline will be conducted using median values. Plots of CSTs for each subject over time will be used to identify associations between CSTs and incidence of CID, mucositis and severity of side effects. In order to model the dynamics of the CST transitions, we will use Markov chain to estimate the transition probabilities, as demonstrated for vaginal CST associated with pre-term birth. Transition rates between CSTs for each set of paired samples will be calculated using maximum-likelihood estimates. Additionally, differential relative abundance analysis of CSTs between baseline (pre-surgery and pre-treatment) and treatment time points will be conducted using linear mixed models to account for the repeated measurements at the 4 time points and missing observations. To evaluate differences in beta diversity between treatment and baseline the PERMANOVA test will be used. The inferred function of the microbiota will be obtained using the bioinformatics tool PICRUSt, which uses 16S rRNA marker genes to predict presence of gene families and construct a composite metagenome. This method has been used successfully in several similar studies to predict key metabolic functions associated with taxa important in distinguishing disease from healthy controls.

**Metabolite-CID analysis:** In a similar manner to the Microbiome-CID analysis, we will conduct logistic regression analysis between CID (present/absent) and metabolites at baseline, and at individual time points controlling for multiple hypothesis testing (FDR  $<0.05$ ). Further, principal component analysis and partial least squares-discriminant analysis will be conducted to determine the metabolic alteration between CID and nonCID subjects after mean centering and unit variance scaling. The variable importance scores of all of the peaks for the tenfold cross-validated PLS-DA model will be considered for

peak selection and biomarker classification. Additionally, metabolites found to be significantly different between treatment time points and baseline will be put into an adjusted linear mixed model regression.

